8.2. Laboratory Test Abnormalities

Laboratory abnormalities that constitute an AE in their own right (considered clinically meaningful, induce clinical signs or symptoms, require concomitant therapy, or require changes in study drug) should be recorded on the Adverse Event form in the eCRF. Whenever possible, a diagnosis rather than a symptom should be provided (eg, "anemia" instead of "low hemoglobin"). Laboratory abnormalities that meet the criteria for AEs should be followed until they have returned to normal or an adequate explanation of the abnormality is found. When an abnormal laboratory test result corresponds to a sign or symptom of a previously reported AE, it is not necessary to separately record the laboratory test result as an additional event.

Laboratory abnormalities that do not meet the definition of an AE should not be reported as AEs. A Grade 3 or 4 AE does not automatically indicate an SAE unless it meets the definition of serious, as defined in Section 8.3.1. A dose modification for the laboratory abnormality may be required (see Section 5.4) and should not contribute to the designation of a laboratory test abnormality as an SAE.

8.3. Serious Adverse Events

8.3.1. Definitions

An SAE is defined as an event that meets at least 1 of the following criteria:

- Is fatal or life-threatening.
- Requires inpatient hospitalization or prolongation of existing hospitalization, unless hospitalization is a result of:
 - A routine treatment or monitoring of the studied indication not associated with any deterioration in condition.
 - An elective surgery or preplanned treatment for a pre-existing condition that is unrelated to the indication under study and has not worsened since signing the ICF.
 - A treatment on an emergency outpatient basis for an event not fulfilling any of the definitions of a SAE and not resulting in hospital admission.
 - Any social reasons and respite care, in the absence of any deterioration in the subject's general condition.

- Results in persistent or significant disability, incapacity, or a substantial disruption of a person's ability to conduct normal life functions.
- Constitutes a congenital anomaly or birth defect.
- Is considered to be an important medical event or a medically significant event that may not result in death, be immediately life-threatening, or require hospitalization but may be considered serious when, based on appropriate medical judgment, the event may jeopardize the subject or may require medical or surgical intervention to prevent 1 of the outcomes listed above.

8.3.2. Reporting

Every SAE, regardless of suspected causality (eg, relationship to study drug(s) or study procedure or disease progression), occurring after the subject has signed the ICF through the last study visit (or 100 days after the last dose of study treatment, or until the subject receives a new anticancer therapy, whichever occurs earlier) must be reported to the sponsor (or designee) within **24 hours** of learning of its occurrence, unless otherwise specified by the Protocol. Any SAEs occurring more than 100 days for Treatment Group A and 150 days for Treatment Group B after the last dose of study drug should be reported to the sponsor or its designee only if the investigator suspects a causal relationship to the study drugs.

Information about all SAEs is collected and recorded on the Adverse Event form of the eCRF. The investigator must assess and record the causal relationship of each SAE to the study treatment. The investigator must also complete the Incyte Serious Adverse Event Report Form, in English, and send the completed and signed form to the sponsor or designee within 24 hours of becoming aware of the SAE. The investigator must provide a causality assessment, that is, assess whether there is at least a reasonable possibility that the SAE is related to the study treatment: suspected (yes) or not suspected (no). Refer to the Incyte Reference Guide for Completing the Serious Adverse Event Report Form.

The contact information of the sponsor's study-specific representatives is listed in the investigator manual provided to each site. The original copy of the SAE Report Form and the confirmation sheet must be kept at the study site.

Investigational site personnel must report any new information regarding the SAE within 24 hours of becoming aware of the information in the same manner that the initial SAE Report Form was sent. Follow-up information is recorded on an amended or new SAE Report Form, with an indication that it is follow-up to the previously reported SAE and the date of the original report. The follow-up report should include information that was not provided on the previous SAE Report Form, such as the outcome of the event (eg, resolved or ongoing), treatment provided, action taken with study drug because of the SAE (eg, dose reduced, interrupted, or discontinued), or subject disposition (eg, continued or withdrew from study participation). Each recurrence, complication, or progression of the original event should be reported as follow-up to that event, regardless of when it occurs.

If the SAE is not documented in the IB for the study drug (new occurrence) and is thought to be related to the sponsor's study drug, the sponsor or its designee may urgently require further information from the investigator for reporting to health authorities. The sponsor or its designee may need to issue an Investigator Notification (IN) to inform all investigators involved in any

study with the same drug that this SAE has been reported. Suspected Unexpected Serious Adverse Reactions (SUSARs) will be collected and reported to the competent authorities and relevant ethics committees in accordance with Directive 2001/20/EC, or as per national regulatory requirements in participating countries.

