5.5.2. Withdrawal Procedures

In the event that the decision is made to permanently discontinue the study drug, the subject will be withdrawn from the study and the EOT visit should be conducted. Reasonable efforts should be made to have the subject return for the safety follow-up visit (see Section 6.4). The last date of the last dose of study drug and the reason for subject withdrawal will be recorded in the eCRF.

If a subject is withdrawn from all study treatment:

- The study monitor or sponsor must be notified.
- The reason(s) for withdrawal must be documented in the subject's medical record and in the eCRF.

Note: The reason for withdrawal from treatment may be different than the reason for withdrawal from study.

- The EOT visit should be performed.
- The date of the EOT visit should be recorded in the eCRF and IRT.
- Subjects must be followed for safety until the time of the follow-up visit or until study drug–related toxicities resolve, return to baseline, or are deemed irreversible, or until the subject begins new anticancer therapy, whichever is longest.

If the subject discontinues study treatment and actively withdraws consent for collection of follow-up data (safety follow-up), then no additional data collection should occur; however, subjects will have the option of withdrawing consent for study treatment but continuing in the safety follow-up period.

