6.4. Follow-Up

6.4.1. Safety Follow-Up

The safety follow-up period is the interval between the EOT visit and the scheduled follow-up visits, which should occur approximately 30 days (+ 7 days), 100 days (\pm 7 days), and 150 days

(± 7 days; Treatment Group B only) after the EOT visit (or after the last dose of study treatment if the EOT visit was not performed). Adverse events and SAEs must be reported up until at least 100 days after the last dose of study treatment for Treatment Group A, up until at least 150 days after the last dose of study treatment for Treatment Group B, or until toxicities resolve, return to baseline, or are deemed irreversible, whichever is longer. Reasonable efforts should be made to have the subject return for the follow-up visits and to report any AEs that may occur during this period. If a subject is scheduled to begin a new anticancer therapy before the end of the safety follow-up period, the applicable safety follow-up visit should be performed before new anticancer therapy is started. After the safety follow-up period, there will be no additional assessments and the study will be considered complete.

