8.1.2. Reporting

Adverse events that begin or worsen after informed consent should be recorded on the Adverse Events form of the eCRF. Conditions that were already present at the time of informed consent should be recorded on the Medical History form in the eCRF. Monitoring for the occurrence of new AEs should be continued for at least 100 days after the last dose of study treatment for Treatment Group A, and 150 after the last dose of study treatment for Treatment Group B. Adverse events (including laboratory abnormalities that constitute AEs) should be described using a diagnosis whenever possible rather than by individual underlying signs and symptoms.

The term "disease progression" should be recorded as an AE/SAE only if there are no other identifiable AEs/SAEs associated with the disease progression at the time of reporting. For events associated with disease progression, the relevant signs and symptoms should be reported using a diagnosis whenever possible rather than individual underlying signs and symptoms. When a clear diagnosis cannot be identified, each sign or symptom should be reported as a separate AE. If the events resulting from disease progression meet the criteria for an SAE (eg, resulted in hospitalization, a life-threatening event, or death), the specific event(s) should be reported as an SAE(s) as described in Section 8.3.2. In both cases (ie, AEs or SAEs related to disease progression), it should be indicated that each event (reported as a diagnosis or as signs and symptoms) is related to disease progression on the Adverse Events form of the eCRF.

The severity of AEs will be assessed using CTCAE v4.03 Grades 1 through 5. If an event is not classified by CTCAE, the severity of the AE will be graded according to the scale below to estimate the grade of severity:

Grade 1	Mild; asymptomatic or mild symptoms; clinical or diagnostic observations only; intervention not indicated.
Grade 2	Moderate; minimal, local, or noninvasive intervention indicated; limiting age-appropriate activities of daily living.
Grade 3	Severe or medically significant but not immediately life-threatening; hospitalization or prolongation of hospitalization indicated; disabling; limiting self-care activities of daily living.
Grade 4	Life-threatening consequences; urgent intervention indicated.
Grade 5	Death due to AE

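### Sections 8.3.2 and 6.4.1 give contradictory SAE reporting windows for Treatment Group A, and Section 8.3.2 on its own sets no expedited-reporting duty for a new related SAE between new anticancer therapy and Day 100

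*Combined protocol and SAP*

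**What the plan says.** Four places in the protocol bear on how long SAEs are reported after the last dose.

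- **Section 8.3.2, first sentence.** Every SAE, whatever its suspected cause, goes to the sponsor within 24 hours of the site learning of it. The period runs from consent and ends at the last visit. Day 100 after the last dose is a second possible end, and new therapy is a third: "or until the subject receives a new anticancer therapy, whichever occurs earlier".
- **Section 8.3.2, second sentence.** "Any SAEs occurring more than 100 days for Treatment Group A and 150 days for Treatment Group B after the last dose of study drug" are reported "only if the investigator suspects a causal relationship to the study drugs".
- **Section 6.4.1.** AEs and SAEs in Treatment Group A must be reported for a minimum of 100 days after the last dose, "or until toxicities resolve, return to baseline, or are deemed irreversible, whichever is longer". New anticancer therapy appears there only as a reason to bring the follow-up visit forward, not as an end to reporting.
- **Section 8.1.2.** "Monitoring for the occurrence of new AEs should be continued for at least 100 days after the last dose of study treatment" in Group A. New therapy is not mentioned.

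Section 5.5.2 covers how long a withdrawn subject is followed for safety. It lists the follow-up visit, resolution of drug-related toxicity, "or until the subject begins new anticancer therapy, whichever is longest".

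**The concern.** One rule takes the earliest of several events and the other takes the latest. For a subject who starts new therapy before Day 100, a site cannot treat both as the SAE window. Section 8.3.2 is where a site would look, because it is the SAE reporting section and holds the 24-hour requirement.

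The second sentence of Section 8.3.2 is meant to keep related SAEs reportable after routine reporting ends. It is tied to Day 100, however, and not to the point at which routine reporting actually stopped. When new therapy stops it sooner, nothing in that section covers the time in between.

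The situation can readily arise. Section 5.6.3 prohibits no therapies during post-treatment follow-up. Section 1.6 expects some immune-related toxicities, such as raised liver enzymes and endocrinopathies, to appear later than others. The sponsor's onward reporting of unexpected serious reactions depends on what investigators send. Under Section 4.5, subjects remaining after an early database lock have their SAEs reported according to Section 8, which contains the gap. Closing enrollment does not remove the problem, because Amendment 2 governs subjects still on treatment.

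**Working it through.** The plan states no figure to reproduce. The check applies each rule day by day after the last dose, for Treatment Group A.

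**Inputs**

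- Routine limit in Section 8.3.2: Day 100, cut short by new therapy or by the last study visit.
- Related-SAE rule in Section 8.3.2: applies from Day 101.
- Minimum in Section 6.4.1: through Day 100, with no cut at new therapy.
- Day t on which new therapy starts: not given in the documents. Values from 14 to 90 are assumed to show the range.

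**Rules**

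- Routine reporting under 8.3.2 covers Days 1 to min(100, t, last visit).
- The related-SAE rule under 8.3.2 covers Day 101 onward.
- If t is below 100 and the last visit does not come sooner, the days covered by neither sentence run from t + 1 to 100. The gap is 100 − t days.

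| Assumed t | Days covered by neither sentence of 8.3.2 | Gap | Gap days on which 6.4.1 requires reporting |
|---|---|---|---|
| 14 | 15 to 100 | 100 − 14 = 86 | 86 |
| 30 | 31 to 100 | 100 − 30 = 70 | 70 |
| 45 | 46 to 100 | 100 − 45 = 55 | 55 |
| 60 | 61 to 100 | 100 − 60 = 40 | 40 |
| 90 | 91 to 100 | 100 − 90 = 10 | 10 |
| none | none, if the last visit is on or after Day 100 | 0 | 0 |

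The last two columns agree in every row: each day that 8.3.2 leaves open is a day on which 6.4.1 requires a report.

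The last-visit limit produces a smaller gap of the same kind. The 100-day visit has a window of ± 7 days. If it takes place on Day 93 (100 − 7, an assumed day) and is the last visit, Days 94 to 100 fall outside both sentences, which is 7 days.

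The ordering is hard to defend as intended. Take t = 30. Under Section 8.3.2 a new SAE on Day 60 that the investigator thinks is drug-related need not be expedited, while a similar event on Day 101 must be.

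**The case against.** The strongest reply is that the protocol as a whole does not exempt these events. Section 6.4.1 requires them to be reported on every gap day. Section 8.1.2 keeps monitoring for new AEs going for the same minimum period. Section 7.5.1 requires all AEs, serious or not, to be recorded in the source documents and eCRF. Section 8.3.2 also requires recurrences, complications and progression of an SAE already reported to be sent in without a time limit. All of this stands. It confines the point to new SAEs and to a site working from Section 8.3.2 alone.

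A second reply is that the first sentence of 8.3.2 allows for exceptions specified elsewhere in the protocol, which might be read as deferring to 6.4.1. The clause does not say so. It could equally qualify only the 24-hour requirement, or permit exceptions that shorten the duty. It does not settle the conflict.

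A reader might go further and infer that late immune-related SAEs are lost from the safety tables, and lost informatively, because subjects who progress or stop for toxicity start new therapy soonest. The documents do not support this. The limit in 8.3.2 governs expedited reports to the sponsor. The recording provisions just cited do not stop at new therapy, and the definition of a treatment-emergent event in Section 9.4.2.1 has no end date. Nothing in the documents says who starts new therapy or when.

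Two other extensions also fail. Section 8.3.2 gives Group B the 100-day routine limit although 150 days is used elsewhere, but no Group B subjects were enrolled, so the mismatch has no practical effect. Section 5.5.2 is not a third version of the same window: its list of events differs from that in 8.3.2, and it concerns following subjects, not reporting SAEs.

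**Conclusion.** The contradiction between Sections 8.3.2 and 6.4.1 is real and should be corrected. Read alone, 8.3.2 leaves 100 − t days after the start of new therapy in which a new, related SAE in Group A carries no expedited-reporting duty. Over the assumed range of t from 14 to 90, that is 86 days down to 10. These figures give the length of the gap for one subject. They say nothing about how many subjects or events are affected, which cannot be worked out from the documents.

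The consequence that can be shown is missed or late expedited reports, and sites applying different rules. Because 6.4.1, 8.1.2 and 7.5.1 still call for reporting or recording, loss from the safety analysis is not established. The conclusion rests on the wording and on sites possibly using 8.3.2 as their working rule. It needs no assumption about event rates.

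**What to change.** 1. State one SAE reporting window for Treatment Group A and use it in Sections 8.3.2, 6.4.1 and 8.1.2. Make Section 5.5.2 consistent with it.
2. In Section 8.3.2, start the related-SAE rule wherever routine reporting ends, not at a fixed Day 100. If the sponsor keeps a cut-off at new anticancer therapy, the rule should begin there. Suspected-related SAEs then remain reportable at all times.
3. If SAEs after new therapy are collected, flag them in the safety tables so that they can be told apart.

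Whether all SAEs, whatever their cause, should be collected after new therapy is a choice for the sponsor. Reconciling the sections does not require it. Footnote b of Table 21 sets the timing of visits, not the SAE window, and need not change.

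The cost is a few words in four sections and, if step 3 applies, one flag. If the longer window is chosen, the sponsor should also look at Section 7.4, which stops recording concomitant medication at new anticancer therapy when that precedes the end of safety follow-up. Later SAEs would otherwise lack that record when causality is judged.

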8.4. Emergency Unblinding of Treatment Assignment

Not applicable.

8.5. Pregnancy

Pregnancy, in and of itself, is not regarded as an AE unless there is suspicion that study drug may have interfered with the effectiveness of a contraceptive medication or method. When a pregnancy has been confirmed in a subject during maternal or paternal exposure to study drug, the following procedures should be followed in order to ensure subject safety:

- The study drug must be discontinued immediately (female subjects only).
- The investigator must complete and submit the Incyte Clinical Trial Pregnancy form to the sponsor or its designee within **24 hours** of learning of the pregnancy.

Data on fetal outcome and breastfeeding are collected for regulatory reporting and drug safety evaluation. Follow-up should be conducted for each pregnancy to determine outcome, including spontaneous or voluntary termination, details of the birth, and the presence or absence of any birth defects, congenital abnormalities, or maternal and/or newborn complications, by following until the first well-baby visit. Pregnancy should be recorded on a Clinical Trial Pregnancy form and reported by the investigator to the sponsor or its designee. Pregnancy follow-up information should be recorded on the same form and should include an assessment of the possible causal relationship to the sponsor's study drug to any pregnancy outcome, as well as follow-up to the first well-baby visit or the duration specified in local regulations, whichever is later. Refer to the Incyte Reference Guide for Completing the Clinical Trial Pregnancy Form.

Any SAE occurring during pregnancy must be recorded on the SAE report form and submitted to the sponsor or designee.

8.6. Warnings and Precautions

Special warnings or precautions for the study drug, derived from safety information collected by the sponsor or its designee, are presented in the Investigator's Brochure (IB). Additional safety information collected between IB updates will be communicated in the form of Investigator Notifications. Any important new safety information should be discussed with the subject during the study, as necessary. If new significant risks are identified, they will be added to the ICF.

8.7. Safety Monitoring Committee

For Phase 1, approximately weekly, the sponsor will conduct telephone conferences with investigators to review dose level-specific data, overall safety data from prior dose levels (if applicable), and to agree on dose escalation, dose de-escalation, and cohort expansion decisions. For Phase 2, a safety monitoring committee (SMC) will review safety data at regular intervals throughout the study. The frequency of meetings will be contingent upon enrollment and

availability of safety data for analysis and review. Details regarding membership, roles, and responsibilities of the committee are specified in the SMC charter.

8.8. Product Complaints

The sponsor collects product complaints on study drugs and drug delivery systems used in clinical studies in order to ensure the safety of study participants, monitor quality, and facilitate process and product improvements.

All product complaints associated with material packaged, labeled, and released by the sponsor or its designee will be reported to the sponsor. All product complaints associated with other study material will be reported directly to the respective manufacturer.

The investigator or his/her designee is responsible for reporting a complete description of the product complaint via email or other written communication to the sponsor contact or respective manufacturer as noted in the packaging information. Any AE associated with a product complaint should be reported as described in Section 8.1.2 of this Protocol.

If the investigator is asked to return the product for investigation, he/she will return a copy of the product complaint communication with the product.

[figure not shown]
9. STATISTICS

9.1. Study Populations

The safety population includes all subjects enrolled in the study who received at least 1 dose of combination therapy (epacadostat, nivolumab, ipilimumab for Treatment Group A, or epacadostat, nivolumab, lirilumab for Treatment Group B). All safety analyses will be based on the safety population.

The full analysis set includes all subjects enrolled in the study who received at least 1 dose of combination therapy (epacadostat, nivolumab, ipilimumab for Treatment Group A, or epacadostat, nivolumab, lirilumab for Treatment Group B). The full analysis set will be used for the summary of demographics, baseline characteristics, subject disposition, and analyses of all efficacy data.

The PP population includes all subjects in the full analysis set that are considered to be sufficiently compliant with the Protocol. More details of the PP population will be provided in the Statistical Analysis Plan. The PP population may be used in the sensitivity analysis of efficacy endpoints. The determination of subjects being considered for exclusion from the PP population by the clinical team will be prepared and signed before database freeze.

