4. INVESTIGATIONAL PLAN

4.1. Overall Study Design

Note: Amendment 2 will serve to close the study to further enrollment; the primary purpose of the amendment is to provide an updated assessment schedule for subjects enrolled to date (Treatment Group A only). No subjects were enrolled into Treatment Group B.

[figure not shown]
This is an open-label, nonrandomized, Phase 1/2 study to determine the safety, tolerability, and efficacy of epacadostat when given in combination with nivolumab and ipilimumab, and in combination with nivolumab and lirilumab. The study will be conducted in 2 independent treatment groups: Treatment Group A will evaluate the combination of epacadostat, nivolumab, and ipilimumab; Treatment Group B will evaluate the combination of epacadostat, nivolumab, and lirilumab. Each treatment group will be investigated in 2 phases:

- Phase 1 will consist of a standard 3 + 3 + 3 dose-escalation design to define the MTD or PAD of epacadostat with nivolumab and ipilimumab (Treatment Group A) and with nivolumab and lirilumab (Treatment Group B) in subjects with advanced or metastatic solid tumors; [REDACTED]
- Phase 2 will evaluate the efficacy of the MTD or PAD of epacadostat when given in combination with nivolumab and ipilimumab, and in combination with nivolumab and lirilumab, as determined in each of the Phase 1 treatment groups in select solid tumors, and will further evaluate the safety, [REDACTED] of the combinations.

Treatment Group A will enroll 2 tumor-specific expansion cohorts (Cohorts A1 and A2); Cohort A1 will include subjects with unresectable or metastatic MEL who have not received prior systemic therapy for advanced or metastatic disease; Cohort A2 will include subjects with advanced or metastatic NSCLC who have received no more than 1 prior line of platinum-based chemotherapy for advanced or metastatic disease.

Treatment Group B will enroll 1 expansion cohort (Cohort B1); Cohort B1 will include subjects with recurrent or metastatic SCCHN who have received no more than 1 prior line of platinum-based chemotherapy for recurrent or metastatic disease. See [Figure 1](#) for overall study design.

Figure 1: Study Design

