4.3.2. Replacement of Subjects

Subjects may be replaced for any of the following reasons:

- In Phase 1, any subject who withdraws from treatment before the completion of the DLT observation period for any reason other than a DLT (ie, is not evaluable for DLTs; see Section 5.4.2) or who does not have the required exposure to the study drugs during the DLT evaluation period, may be replaced to ensure a minimum number of evaluable subjects.
- Subjects who do not meet the eligibility requirements of the study may be replaced.

Subjects who meet any of the criteria for replacement may remain on study for evaluation as outlined in Section 9.1 and Section 9.2.

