9.4.2. Safety Analyses

The clinical safety data (vital signs, physical examinations, ECGs, laboratory tests, and AEs) will be summarized using descriptive statistics (eg, mean, frequency) using the safety population. Summary tables may be replaced with listings when appropriate. For example, an AE frequency table may be replaced with a listing if it only contains a few unique preferred terms reported on relatively few subjects.

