9.4.2.1. Adverse Events

A TEAE is any AE either reported for the first time or worsening of a pre-existing event after first dose of study treatment. Analysis of AEs will be limited to TEAEs, but data listings will include all AEs regardless of their timing to study drug administration. Adverse events will be tabulated by the MedDRA preferred term and system organ class. Severity of AEs will be based on the NCI CTCAE v4.03 using Grades 1 through 5.

The subset of AEs considered by the investigator to have a relationship to study drug will be considered to be treatment-related AEs. If the investigator does not specify the relationship of

the AE to study drug, the AE will be considered treatment-related. The incidence of AEs and treatment-related AEs will be tabulated.

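### Does Section 9.1 drop from the safety tables a Group A subject whom toxicity stops before ipilimumab?

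*Combined protocol and SAP*

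**What the plan says.** Section 9.1 (Study Populations) sets the rule: "The safety population includes all subjects enrolled in the study who received at least 1 dose of combination therapy (epacadostat, nivolumab, ipilimumab". That is the Group A list; in Group B lirilumab replaces ipilimumab. The section continues: "All safety analyses will be based on the safety population". Section 9.4.2 repeats that the clinical safety data "will be summarized using descriptive statistics (eg, mean, frequency) using the safety population". The full analysis set is defined in the same terms. Section 9.1 leaves details to the Statistical Analysis Plan only for the per-protocol population.

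Section 9.4.2.1 starts the clock differently: "A TEAE is any AE either reported for the first time or worsening of a pre-existing event after first dose of study treatment". It adds that "data listings will include all AEs regardless of their timing to study drug administration".

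Section 4.3.2 allows replacement of a Phase 1 subject "who does not have the required exposure to the study drugs during the DLT evaluation period, may be replaced", and then says: "Subjects who meet any of the criteria for replacement may remain on study for evaluation as outlined in Section 9.1 and Section 9.2".

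**The concern.** Section 9.1 contains neither an 'any' nor an 'all'. Section 4.1 uses the word combination for the three drugs together: "Treatment Group A will evaluate the combination of epacadostat, nivolumab, and ipilimumab". If that sense is carried into Section 9.1, a subject must have had all three drugs to enter the safety population.

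The drugs are not given at the same moment. On Cycle 1 Day 1 epacadostat comes before any infusion (Section 5.2.1), nivolumab follows (Section 5.2.2.1), and ipilimumab starts at least 30 minutes after nivolumab ends (Section 5.2.3.1). Table 18 ends all study treatment after a Grade 3 or 4 infusion reaction. A subject who reacts in this way to nivolumab has taken study drug and has a treatment-emergent event, yet on the strict reading is outside the population because of that event. An exclusion driven by the outcome lowers the reported rates.

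Safety is the Phase 1 primary objective, dose levels hold 3 to 9 subjects, and after Amendment 2 selected safety tables are the only summary tables still planned (Section 9.4).

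**Working it through.** The plan gives no figure to reproduce. The check has two parts: which reading the text supports, and how far the strict reading could reach.

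**Which reading the text supports**

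1. The parenthesis in Section 9.1 is organised by treatment group, and its only 'or' separates Group A from Group B. It identifies a regimen and sets no minimum exposure.
2. The components run on different schedules: twice daily, every cycle and every third cycle. One dose of a three-drug combination is therefore not a defined unit, which points to a loose label.
3. The term is loose elsewhere. Section 9.4.1 measures progression-free survival from the start of the combination, which reads naturally as the start of the regimen. The synopsis uses combination therapy as a heading for the infused antibodies alone, with epacadostat under its own heading.
4. Where minimum doses per drug are intended, they are written out. Section 5.4.2 asks Group A subjects for 63 of 84 epacadostat doses, 3 of nivolumab and 1 of ipilimumab, unless a DLT occurs. Section 9.1 has nothing of the kind.
5. Section 4.3.2 sends subjects who lack the required exposure to Section 9.1 for evaluation. This points back to the same wording, so it proves nothing alone, but it fits inclusion better than exclusion.
6. The treatment-emergent definition starts at the first dose of study treatment and does not wait for a third drug.

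An any-drug rule also disposes of the half-finished infusion: a subject who took epacadostat first, as Section 5.2.1 requires, already qualifies.

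**How far the strict reading could reach**

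All three drugs start on Cycle 1 Day 1, so the documented route is a Grade 3 or 4 reaction to the first nivolumab infusion. After a Grade 2 reaction, Table 18 allows a restart or a later dose.

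Suppose x of n subjects have an event and one of the x is left out. The reported proportion falls by

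x/n − (x − 1)/(n − 1) = (n − x) / [n(n − 1)].

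The event counts below are assumptions. The first two cases take the omitted subject as the only case and assume tables by dose level, at the 3 + 3 + 3 sizes.

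| Case | Included | Left out |
|---|---|---|
| Not a DLT, subject replaced | 1/4 = 25.0% | 0/3 |
| | 1/7 = 14.3% | 0/6 |
| | 1/10 = 10.0% | 0/9 |
| DLT, not replaced | 1/3 = 33.3% | 0/2 |
| | 1/6 = 16.7% | 0/5 |
| | 1/9 = 11.1% | 0/8 |
| Phase 1 pooled, about 18 planned, 6 events | 6/18 = 33.3% | 5/17 = 29.4% |

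For the pooled row, (18 − 6)/(18 × 17) = 12/306 = 3.9 points. An example of the first case is a Grade 3 infusion reaction that returns to Grade 1 in under 6 hours, which Table 7 exempts from the DLT definition. In the second case the DLT tally stays at 1/3, 1/6 or 1/9 on either reading.

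Sections 9.4.2 and 9.4.2.1 do not say that adverse event tables are split by dose level, so the larger movements rest on a layout the plan does not state.

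**The case for a change.** The best argument for a change is that a denominator should be settled in writing before anyone knows whom it affects. Nothing in the documents expressly settles it. Section 5.4.1 shows that the authors could refer to any single treatment component when they wished, and Section 9.1 does not. On the strict reading one subject could count in the DLT tally and be missing from the adverse event table. The promise of full listings concerns the timing of events, so it does not plainly cover a subject outside the population. Section 4.1.1 also mentions sequenced dosing as a possible alternative schedule, which would widen the window before the third drug. The remedy would be one sentence.

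The ambiguity and the low cost stand. What does not follow is that the plan prescribes a wrong analysis. The harm needs the less natural reading, an affected subject, and an analyst who would exclude a treated subject from a safety table. The documents show none of these, and nothing shows that sequenced dosing was used.

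**Conclusion.** No change follows. Section 9.1 leaves a detail unstated, and analysts would fill it with the standard rule that one dose of any study drug is enough, which the treatment-emergent definition already implies.

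The practical stake is small. Enrollment is closed, so any affected subject already exists, and the number may be zero. Escalation decisions follow the DLT rule, under which a subject with a DLT is evaluable without the minimum doses. Serious events are reported from consent onwards (Section 8.3.2). Section 9.4.2 allows a sparse table to be replaced by a listing. The full analysis set shares the wording, but Amendment 2 replaces efficacy summary tables with listings, so no response-rate summary table depends on it.

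This conclusion assumes the standard Cycle 1 Day 1 schedule and the any-drug reading. The percentages above describe an invented case and do not measure an error in the plan. The text of the separate Statistical Analysis Plan that the protocol mentions is not available here and may already state the rule.
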